9.0 Outcome Measures

9.1 Primary outcome measure

The primary outcome measures are:

- 1. The proportion of patients that have a rise in interferon gamma levels within the tumor microenvironment of 4 pg/ml or higher before the first dose of Nivolumab as compared to the 5th day after treatment with Nivolumab.
- 2. The safety of the use of microdialysis catheters for immune monitoring in recurrent glioblastoma patients
- 3. The safety of the combination of nivolumab and BMS-986016 in recurrent glioblastoma patients

9.2 Exploratory outcome measures

Exploratory outcome measures and include:

- 1. The change in interferon gamma expression from before, during and after Nivolumab treatment in the brain microenvironment, cerebral spinal fluid and the blood.
- 2. The difference between the IHC staining for CD3, CD4, CD8, CD20, CD45RO, CD57, CD68, FOXP3, Granzyme B, LAG3, PD-1, CD14, CD33, CD163, and CD206 before and after Nivolumab therapy. These markers will be evaluated as density of cells, defined as the number of positive cells per mm². PD-L1 expression will be evaluated in tumor cells using H-score, which includes the percentage of positive cells showing membrane staining pattern (0–100) multiplied by the intensity of the staining (0 to 3+), with a total score ranging from 0 to 300. The final score for each marker will be expressed as the average score of the areas analyzed within the tumor region (tumor center).
- 3. Progression free survival and overall survival of recurrent glioblastoma patients after treatment. Progression free survival is defined as the time length from the first dose of study drug with recurrence to progression as defined by iRANO criteria, and the overall survival is defined as the time length from the first dose of study drug to death. If a lesion is 25% larger but there remains a question as to disease progression or pseudoprogression due to treatment, the patient can remain on treatment until this can be defined. If true progression occurred earlier, the earlier date will be used for censorship. If patient is lost to follow-up prior to documented progression or death, patient will be censored as of the date of the last adequate evaluation (MRI and exam). If patient dies prior to documentation of progression, progression will be defined as the date of death, if patient has been attending regularly scheduled follow-ups.
- 4. The difference in progression free survival and overall survival between patients who have an interferon gamma response versus those that do not have one.

5. The difference in the immune cells and secreted factors of the tumor environment as compared to the immune cells and secreted factors of the cerebral spinal fluid, blood and potential bone marrow in response to this treatment

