systemic checkpoint inhibitor therapy. Patients will undergo a surgical procedure that includes brain tumor needle biopsy to confirm the diagnosis of recurrent glioblastoma. If the diagnosis of recurrent glioblastoma is confirmed by frozen section, they will proceed with the remainder of the protocol. If this diagnosis cannot be definitively confirmed on frozen section, the patient will not proceed with the placement of microdialysis catheters or lumbar drain. If the patient does have frozen section evidence of recurrent glioblastoma, 2 microdialysis catheters will be implanted, one into the tumor, and one into the surrounding brain. A lumbar intrathecal catheter will also be inserted to serial sample cerebral spinal fluid (CSF). A bone marrow examination may be performed to evaluate the baseline status of the patients' hematopoietic tissue. To allow the inflammatory response to catheter implantation to subside, we will wait two days after surgery before administering the PD-1 inhibitor, Nivolumab. We will then take samples every 6 hours from the microdialysis catheters, and daily samples from blood and cerebral spinal fluid. At the end of five days, we will remove the dialysis catheters and lumbar intrathecal catheter and resect the recurrent glioblastoma tumors. A repeat bone marrow examination may be performed to evaluate if Nivolumab causes any changes in the patients' hematopoietic tissue. Following tumor resection, the patient will receive Nivolumab and an anti-LAG-3 antibody, BMS-986016, until tumor progression or until the patient experiences an immune mediated toxicity that prevents further treatment, as defined in Appendix A. We will analyze the cerebral spinal fluid, microdialysis fluid and blood for immune markers by proteomic analysis. We will measure changes in immune markers in the various compartments (brain tumor, brain, blood, CSF and potentially bone marrow) between before and after their first dose of nivolumab and determine the relative immune effects of Nivolumab in these compartments. Recent data in melanoma patients suggests that after a month of treatment, changes in histological markers of immune response such as cluster of differentiation 8 (CD8), CD4, CD3, PD-1, PD-L1 and lymphocyte activation gene 3 (LAG3) may be predictive of response to PD-1 inhibitors[37]. As such, if we are unable to establish interferon gamma as a suitable marker of immune response, we will evaluate pathological response as our primary outcome measure.

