4.4 Study Design

This protocol is an open label, non-blinded single armed pilot study of the use of nivolumab and BMS-986016 in recurrent glioblastoma patients.

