4.5.10.5 Microdialyis catheter placement (Research)

After the brain biopsy is performed confirming recurrent glioblastoma, the neuronavigation system will be utilized to plan a needle trajectory from two skull burr holes to the dialysis probe targets. The MD 71 catheter we will implant has one inlet and one outlet tube which is designed for sampling only. The surgeon's discretion will be used to pick solid, contrast-enhancing portions of the lesion that appear to best represent the most pathological portion of the tumor for microdialysis catheter placement. The surgeon's discretion will also be used to pick a second site that does not appear to be contrast-enhancing tumor for the peritumoral catheter. A stab incision on the scalp will be made at the site of each planned burr hole, one planned to go into the contrast enhancing tumor, and one into the peri-tumoral area, at least 10mm away from the contrast enhancing margin of the tumor, using neuronavigation system guidance as above. This will be done using the surgeon's discretion. We will assess the peritumoral catheter target using the following criteria:

- 1) A lack of contrast-enhancement as noted on the neuronavigation system
- 2) The closest adequate area to the tumor site, as assessed by the surgeon
- 3) Adequate brain tissue surrounding the placement site to allow the catheter to sit in the tissue undisturbed, as assessed by the surgeon
- 4) A safe path to the insertion site, as assessed by the surgeon

Once the dura and pial surface are pierced, as above, the catheter will be passed along the established trajectory into the brain tissue. A guide needle may be used to place the microdialysis catheter. The part of the catheter outside the skull will be tunneled under the skin to a second stab incision, where it will exit the scalp. The ends of the tubing connected to the cannulas will be sterilely sealed and secured. The scalp wound will be closed, and the head frame removed while anesthetized. Patients will be awakened from anesthesia and returned to the Intensive Care Unit for immediate postoperative care. The dialysis machines will be attached to each catheter in the ICU.

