5.1 Sample Storage

All collected research samples, including surgical tumor specimens, CSF, microdialysate, and blood will be coded and stored in secured freezers on the NIH campus. All patients enrolled in this protocol will be assigned a sequential code and all biological samples collected for this patient will be labeled with the patient's code, date of collection, type of sample, sample number, and barcode which will be linked back to relevant sample information in the study laboratory notebooks and Labmatrix. The study samples may be shared with collaborators that have a research interest in the coded samples. Only the study investigators will have access to the code key.

Loss or destruction of samples that impacts the care or safety of human subjects will be immediately reported to the IRB. Loss or destruction of samples that would not impact the care or safety of human subjects but would impact the acquisition of knowledge, will reported to the IRB within 7 days of each occurrence.

Samples collected from patients enrolled at the Emory University site will be transferred to the NIH laboratory prior to primary analysis in accordance with technology transfer and/or Sponsor's trial agreement documents.

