10.0 Statistical Analysis

10.1 Data analysis

Primary goals

- To determine the proportion of patients who have an increase of interferon gamma production within the tumor microenvironment from before and after therapy with the immune checkpoint inhibitor, nivolumab. The change will be dichotomized as increase vs. no increase with the threshold of 4pg/ml. The proportion of the patients with increase will be evaluated by exact binomial test.
- To evaluate the safety of using brain tumor microdialysis to monitor response to immune modulators in patients with recurrent glioblastoma.
 Descriptive statistics, such as frequency and percentage, will be used to evaluate the safety of these procedures.
- To evaluate the safety of the combination of Nivolumab and BMS-986-016 in the treatment of recurrent glioblastoma patients.
 Descriptive statistics, such as frequency and percentage, will be used to evaluate the safety of these treatments.

Exploratory Goals

1) To determine the change in interferon gamma production within the tumor microenvironment and in the rest of the body from before and after therapy with the immune checkpoint inhibitor, nivolumab.

A one-sample t-test or Wilcoxon signed rank test will be performed to evaluate the change (continuous) over time (between pre- and post-treatment) in the outcome measures

2) To evaluate the pathological response of the immune microenvironment of brain tumor tissue to the first dose of Nivolumab

A one-sample t-test or Wilcoxon signed rank test will be performed to evaluate the change between pre- and post-treatment for each marker evaluated.

3) To evaluate the clinical response (progression free survival, overall survival) of recurrent glioblastoma patients to this treatment

The Kaplan-Meier method will be used to estimate the survival function and generate survival curves. The study is not powered to detect significant differences in survival between the patients in this cohort and historical controls.

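### The pre/post tissue comparison credits change to the first nivolumab dose, but biopsy and catheter injury fall in the same interval and nothing in the plan separates them

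*Combined protocol and SAP*

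**What the plan says.** Section 10.1, Exploratory Goal 2, sets the aim: "To evaluate the pathological response of the immune microenvironment of brain tumor tissue to the first dose of Nivolumab". The method follows: "A one-sample t-test or Wilcoxon signed rank test will be performed to evaluate the change between pre- and post-treatment for each marker evaluated". Section 9.2, item 2, lists 15 cell-density markers plus a PD-L1 H-score and states the scoring rule: "The final score for each marker will be expressed as the average score of the areas analyzed within the tumor region (tumor center"). The rule is written for all scores, at both time points.

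Section 4.4 describes the trial as an "open label, non-blinded single armed pilot study". Section 3.1 targets 10 completed patients.

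The only tumor tissue taken before the first dose is the Day 1 stereotactic biopsy, with 4 to 20 samples (Section 4.5.10.4). The microdialysis catheters are placed after it. For the tumor catheter, Section 4.5.10.5 has the surgeon "pick solid, contrast-enhancing portions of the lesion that appear to best represent the most pathological portion of the tumor for microdialysis catheter placement". The catheters run for about 7 days (Section 4.5.12). Nivolumab is given 48 hours after the biopsy, and resection follows 7 days after the biopsy (Section 4.5.1).

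Section 1.8 recognizes that implantation causes inflammation: "To allow the inflammatory response to catheter implantation to subside, we will wait two days after surgery" before dosing. The same section says pathological response will be the primary outcome if interferon gamma cannot be established as a suitable marker.

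**The concern.** A single-arm before/after comparison attributes to the drug everything that happens between the two samples. Here that includes a drug dose and two mechanical injuries to the tumor. Several of the listed markers (CD68, CD163, CD206, CD14, CD3, CD8) mark macrophage, myeloid or T cells, which an injury reaction could also recruit. If they rise, the planned test cannot say why.

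The exploratory label limits the damage only while the endpoint stays exploratory. Under the fallback in Section 1.8, this comparison could carry the trial's main conclusion about whether a systemic checkpoint inhibitor acts inside the tumor.

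**Working it through.** **Step 1. Order of events.**

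| Study day | Event | Effect on the tissue comparison |
|---|---|---|
| 1 | Needle biopsy, 4 to 20 samples | Baseline tissue obtained; first injury |
| 1, after biopsy | Tumor and peritumoral catheters placed | Second injury, after the baseline |
| 3 | First nivolumab dose | The effect the plan wants to measure |
| 8 | Resection | Post-treatment tissue |

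The observed change is therefore (drug effect) + (injury effect) + (time and location differences). With one arm and one post-treatment sample, only the sum can be estimated.

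**Step 2. What the two-day wait protects.** Microdialysis is sampled after implantation and before dosing, so the wait can let that baseline settle. The tissue baseline is taken before implantation. It contains no catheter reaction however long the wait, whereas the Day 8 tissue may contain one.

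**Step 3. Search for other protection.** No section requires the tract position to be recorded for research blocks, keeps scored areas away from a tract, provides tissue from patients who had the procedures without the drug, specifies masked scoring, or qualifies the attribution to nivolumab.

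**Step 4. Possible size.** The plan gives no alpha, sidedness, SD or effect size for this analysis, so it has no figure to reproduce. Assumptions: n = 10, two-sided alpha 0.05, normally distributed within-patient changes, zero drug effect, and an injury shift of d standard deviations of the within-patient change.

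For the one-sample t-test, t = mean / (SD/√10) then follows a noncentral t distribution with 9 degrees of freedom and noncentrality d × √10. The chance of a significant result is P(|t| > 2.262). The Wilcoxon figures come from 4,000 simulations for each d.

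| d (assumed) | d × √10 | t-test | Wilcoxon |
|---|---|---|---|
| 0 | 0 | 0.05 | 0.04 |
| 0.25 | 0.79 | 0.11 | 0.10 |
| 0.5 | 1.58 | 0.29 | 0.29 |
| 0.75 | 2.37 | 0.56 | 0.53 |
| 1.0 | 3.16 | 0.80 | 0.79 |
| 1.5 | 4.74 | 0.99 | 0.98 |

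These are rates for one marker. The extreme case is injury moving a marker in the same direction in all 10 patients. The two-sided signed-rank p-value is then 2 × 0.5^10 = 0.00195, the smallest attainable at n = 10. That is a bound, not an expectation.

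**The case against.** The strongest reply is that this is an exploratory measure in a declared single-arm pilot, where the lack of an untreated comparison is inherent. That is fair as far as the missing control goes. It does not excuse an unqualified attribution to the drug, and the fallback in Section 1.8 takes the endpoint beyond exploratory use.

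A reader might also infer more than the documents support.

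- *That post-treatment tissue is scored where the needle and catheter were.* This is not stated. The catheter site is the surgeon's choice within solid enhancing tumor. The biopsy burr hole is described separately from the two catheter burr holes, and biopsies may come from different sites. Overlap with the scored tumor center is plausible but inferred.
- *That wound inflammation by itself will produce a response.* The documents support only that it could. At d = 0.25 it usually would not reach significance, and they give no basis for expecting all 16 markers to move together, including CD20, FOXP3, CD57 and PD-L1 on tumor cells.
- *That the scorer knows which sample is post-treatment.* Section 5.1 says samples are "labeled with the patient's code, date of collection, type of sample, sample number, and barcode", but that concerns storage. Sample type there may mean only tumor, CSF, dialysate or blood, and Section 5.2 says research data are coded for analysis. What stands is that masked scoring is not specified.

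Finally, a hard exclusion zone around the tracts would create its own problem. Baseline tissue comes only from biopsy sites, so distant post-treatment tissue would never match it in location, and Section 1.4 calls PD-L1 expression heterogeneous. The 10 mm in Section 4.5.10.5 is a clearance from the enhancing margin for the peritumoral catheter, so it cannot simply be borrowed. Both objections stand and shape the remedy.

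**Conclusion.** The point holds in limited form. As written, the tissue comparison cannot separate the first nivolumab dose from biopsy and catheter injury, and the plan attributes the change to nivolumab without a safeguard or caveat. Following it exactly could lead to injury being reported as a drug response.

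How often depends on a quantity the documents do not give. Under the assumptions above, the single-marker rate runs from about 11% (0.25 SD) through 29% (0.5 SD) to 80% (1.0 SD), against a nominal 5%. The confounding itself follows from the order of events and needs no assumption about size; what is uncertain is whether the injury effect is large enough to matter in the areas scored.

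It would go too far to say that the comparison is worthless or that a change would necessarily be wound reaction. It can describe what happened to the tissue over the week. The possible promotion to primary outcome is why this should be corrected rather than merely noted.

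**What to change.** 1. **Mask the scoring.** Score coded image fields from both time points in random order, with collection date and sample type hidden. Cost: recoding of images.
2. **Record position where feasible.** Note each research block's location relative to the biopsy and catheter tracts, using the post-placement CT (Section 4.5.11) and navigation when it is used at resection; Section 4.5.2 provides for stereotaxis only as needed. Cost: added labeling in the operating room and pathology. Research tissue is what neuropathology leaves over (Section 4.5.18), so some blocks may not be mappable.
3. **Prespecify a near- versus far-from-tract sensitivity analysis.** Justify the distance in advance and do not use a fixed 10 mm exclusion. Report estimates with confidence intervals for both zones, since few far areas may be available and a non-significant far result is weak evidence of no effect. State the possible location mismatch with the biopsy baseline as a limitation.
4. **Correct the attribution.** In Sections 2.2, 9.2 and 10.1, describe the result as change after biopsy, catheter and nivolumab. Attribute it to nivolumab only if it persists in far-from-tract tissue, and apply the same condition if the Section 1.8 fallback is used.

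No extra patient, procedure or change in sample size is needed. The main downside is fewer evaluable far-from-tract areas, especially in small tumors or after many biopsy samples.

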Subjects initially meeting radiologic criteria for disease progression may continue receiving study medication until confirmation of progression. Progression will be defined by Response Assessment in Neuro-Oncology Criteria (RANO) criteria, as it has been adopted for immunotherapy trials[38]. The initial radiological suspicion of progression will be raised when:

 $- \ge 25\%$ \uparrow sum of biperpendicular diameters of enhancing disease (new lesions will be added to the sum of the diameter of enhancing disease during the treatment period and will not automatically be assumed to be progression).

This continuation of therapy can continue for a total of 12 weeks with MRIs performed every 4 weeks, as per protocol. iRANO criteria has suggested that this treatment extension only be implemented during the first 6 months of therapy, however there is not yet enough data about treatment of recurrent glioblastoma patients with checkpoint inhibition to be sure of the time course of pseudoprogression. As such, this additional observation period will be implemented at any time while patients are on study medications. Patients will only be eligible to continue therapy in the face of MRI evidence of potential progression if the patient is believed to be demonstrating clinical benefit as deemed by the investigator, the patient is tolerating the study medications and the patient has not significantly declined, neurologically. Of note, if the patient's decline reverses with corticosteroids or surgical sampling of the patient's mass demonstrates treatment effect only, the patient may continue on therapy or resume therapy.

Subjects with confirmed radiologic progression (approximately 12 weeks after initially assessed progression) will discontinue study medication and enter the survival follow up phase of the study. If progression is confirmed, then the date of disease progression will be the first date the subject met the criteria for progression.

To determine clinical progression, subjects with neurological decline will receive a clinical MRI to evaluate for progression by imaging (standard of care).

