During Phase 2, in any patient with significant neurologic decline where disease progression cannot be differentiated from pseudoprogression, and/or in n those cases in which radiologic progression cannot be differentiated from pseudoprogression and it is the investigator's opinion that a surgical biopsy or resection to obtain tumor tissue for histopathology is in the subject's best interests, a surgical resection may be performed following consultation with the medical monitor and outside consultant neurosurgeon. If tumor pathology confirms progression, then the subject will be discontinued from study medication per protocol discontinuation criteria and the date of progression will be the day that it was first suspected. If the patient's decline reverses with corticosteroids and/or tumor pathology reveals treatment-related changes and does not confirm disease progression, we will discuss resumption of therapy with our Safety Monitoring Committee (for patients enrolled at NIH) and the Data and Safety Monitoring Board (for patients enrolled at the Emory Site). The subject will then continue all on-treatment tumor assessments as per the treatment schedule.

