If study drug is discontinued, the patient will enter the survival follow-up phase of the study.

Additionally, if a patient is removed from the study for clinical or radiological progression of disease, we will perform a follow-up assessment at the next scheduled imaging visit and no less than 4 weeks after the prior assessment of disease progression.

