16.2 Reporting of protocol deviations

For safety monitoring, during the microdialysis monitoring period and during subsequent protocol visits, safety checks performed within +/- 5 minutes of stated guidelines will not be considered protocol violations. More than two missed safety checks during infusion monitoring during the microdialysis monitoring period in Phase 1 of the study or during any individual subsequent infusion during Phase 2 of the study will be considered a protocol deviation.

Patients who miss one or more doses of study drug due to treatment of inflammatory side effects will not be censored if these side effects are mild and/or treatable (Grade 1 or 2). Such patients will continue on the study drug when this is safe. This will not be considered a study deviation. Patients who miss one visit will be counseled that further missed follow-up will cause for them to be removed from the Nivolumab and BMS-986016 treatment portion of the trial. Patients that miss two or more consecutive treatments with Nivolumab and BMS-986016 will be censored at the time that they are lost to follow-up. These would be reported as study deviations. We do not expect omissions such as these to affect the primary study outcomes, as these are focusing on the effects of the treatment in the immediate post-surgical period. Based on our experience working with the Neuro-oncology Branch in this patient population, we do not expect to lose many patients in this treatment period.

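### The exploratory PFS rules conflict on deaths without documented progression, on whether a backdated progression is an event, and on the censoring date for patients lost to follow-up

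*Combined protocol and SAP*

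**What the plan says.** Section 9.2 defines PFS as time from first dose of study drug to progression by iRANO, and section 10.1 estimates it by Kaplan-Meier. The rules for events and censoring are spread over several sections.

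- **Death without documented progression.** Sections 9.2 and 4.5.20 both say "progression will be defined as the date of death, if patient has been attending regularly scheduled follow-ups". Neither says what counts as regular, nor what happens to other deaths.
- **Backdated progression.** Section 9.2: "If true progression occurred earlier, the earlier date will be used for censorship". Section 4.5.19, for confirmed radiologic progression: "the date of disease progression will be the first date the subject met the criteria for progression". The same section, for progression confirmed by pathology: "the date of progression will be the day that it was first suspected".
- **Loss to follow-up.** Sections 9.2 and 4.5.20 censor at the last evaluation with an adequate MRI and examination. Section 16.2: "Patients that miss two or more consecutive treatments with Nivolumab and BMS-986016 will be censored at the time that they are lost to follow-up".
- **Follow-up after treatment stops.** Section 8.6: "If study drug is discontinued, the patient will enter the survival follow-up phase of the study". Section 4.7 continues that phase until death and seeks vital status. The calendar in section 25.0 lists only telephone or record follow-up for it, though NIH patients may have further data through 03-N-0164.

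**The concern.** Whether a death counts as a PFS event should not depend on how well the patient attended. Patients with recurrent glioblastoma may miss visits because they are declining. If so, leaving out their deaths, or censoring them earlier under the loss rule, removes early failures and tends to lengthen the PFS curve. The clause is also hard to apply to a patient who stops drug before progression. That patient moves to survival follow-up, and the text does not say whether telephone contact is attendance.

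The other two conflicts let two analysts code the same patient differently: as event or censored (9.2 against 4.5.19), or censored on different dates (9.2 and 4.5.20 against 16.2). The curve will be reported, and section 9.2 also compares PFS and OS by interferon gamma response. At the expected response proportion of 0.7 in section 10.2, that is about 7 patients against 3, so one recoded patient shows.

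**Working it through.** The plan states no PFS median, event count or loss share, so it has no figure to reproduce. The conflicts are textual. The arithmetic only illustrates how much they could matter.

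**1. How far apart the two loss dates can be.** Treatment is every 14 days and MRI every second visit (sections 4.5.9 and 25.0), ignoring visit windows. The last MRI was therefore at the last attended visit or 14 days before it. Section 16.2 does not date the loss:
- at the last attended visit: 0 or 14 days after the last MRI;
- at the first missed visit: 14 or 28 days;
- at the second missed visit: 28 or 42 days.

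The range is 0 to 42 days.

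**2. Ten-patient example (assumed times).** Events fall at 1, 1.5, 2, 2.5, 3, 3.5, 4, 5, 6 and 8 months. With all ten as events, S(3) = 5/10, so the median is 3.0. In the early-censoring and loss-date cases the 1-month patient always stays an event, which leaves 9 patients who could be affected.

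*Censoring 28 days early* (one MRI interval, about 0.92 month). For the 2-month patient, censored at 1.08: S = 9/10 × 7/8 × 6/7 × 5/6 = 0.5625 at 3 months, then × 4/5 = 0.45 at 3.5. The median becomes 3.5.
- One patient: 3.5 in 4 of 9 cases, otherwise 3.0.
- Two patients: 3.0, 3.5 or 4.0 in 10, 16 and 10 of 36.
- Three patients: 3.0, 3.5, 4.0 or 5.0 in 10, 29, 39 and 6 of 84.

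*Section 9.2 taken literally* (one progression coded as censored on its own date). For the 2-month patient: S = 0.9 × 8/9 × 6/7 × 5/6 = 0.571 at 3 months, then × 4/5 = 0.457 at 3.5. The median is 3.5 in 5 of 10 cases. If 4.5.19 governs, nothing changes.

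*Loss date alone* (censored just before the event against 42 days earlier). The median differs in 0 of 9 cases (one patient), 1 of 36 (two) and 14 of 84 (three). A 14-day gap never changes it.

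**3. Large-sample illustration.** PFS is assumed exponential. A share of patients is selected and censored 28 days before the event, only where the event falls more than 28 days after first dose. The table gives the Kaplan-Meier median divided by the true median.

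| Share selected | Median 2 mo | 3 mo | 6 mo |
|---|---|---|---|
| 10% | 1.037 | 1.059 | 1.084 |
| 20% | 1.084 | 1.133 | 1.188 |
| 30% | 1.144 | 1.228 | 1.323 |

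Selected patients with earlier events stay as events, so 30% selected means about 22 to 27% censored. If loss is unrelated to outcome, the ratio is 0.999 to 1.001.

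**4. The remedy has a bias of its own.** In the ten-patient example, suppose one patient's progression is unseen and the later death is counted instead. A death 28, 42 or 56 days after the progression raises the median in 2, 3 or 4 of 9 cases (mean median 3.10, 3.15 or 3.20). Censoring 28 days before progression raises it in 4 of 9 (mean 3.22).

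**The case against.** PFS and OS are exploratory, the trial has one arm with a target of 10 completed patients, and section 10.1 says it is not powered for survival comparisons with historical controls. In the ten-patient example the exact interval for the median (2nd to 9th ordered time, coverage 1 − 22/1024 = 97.9%) is 1.5 to 6.0 months, so a shift from 3.0 to 3.5 is well inside the noise. That stands, and it limits the weight of the point.

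Safeguards also reduce missed progressions. Neurological decline prompts an MRI (4.5.19), unscheduled visits can be arranged (8.1.2), remote visits are foreseen when travel is precluded, and few losses are expected (16.2). They do not supply the missing rules.

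The conflict between 9.2 and 4.5.19 rests on one word. Section 9.2 itself defines PFS as time to progression, so a slip is the natural explanation. A reader might infer that the plan will censor its progressions; the documents as a whole do not support that. The sentence still needs correcting, because followed literally it does so.

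A reader might also infer from 16.2 that a patient who misses two treatments is censored while still being followed. Some text allows this: after one missed visit, "further missed follow-up will cause for them to be removed from the Nivolumab and BMS-986016 treatment portion of the trial", and 8.6 keeps patients off drug in survival follow-up. But 16.2 ties censoring to being lost and names no endpoint, so this is an ambiguity, not an established rule.

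Finally, censoring a death after a long gap without assessment is a defensible choice, and counting it has the cost shown above. That supports a sensitivity analysis; it does not justify an undefined attendance condition.

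**Conclusion.** The point holds as a conflict in the exploratory PFS rules. Two parts can change whether a patient is an event: the attendance condition on deaths and, if read literally, the censoring sentence in 9.2. The loss-date difference is real, but alone it seldom moves the median.

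The direction for deaths is towards longer PFS, provided missed attendance is linked to decline. The size cannot be derived from the documents. The illustrative inflation of about 4 to 32% rests on an assumed exponential PFS with a median of 2 to 6 months, 10 to 30% of patients selected, a 28-day lead and loss fully tied to outcome. It is about zero if loss is unrelated to outcome.

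A reader might infer that OS is biased too, because the loss rule in 9.2 does not separate PFS from OS. The documents do not establish that: OS is defined to death and survival follow-up runs until death, so this is unclear wording only. The interferon gamma outcome is not affected. The rules should be corrected before analysis, but no conclusion on that outcome depends on them.

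**What to change.** Use one set of rules in 4.5.19, 4.5.20, 9.2 and 16.2:

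- PFS event: progression confirmed under the protocol (radiologic, clinical or pathologic) or death from any cause, regardless of attendance.
- In 9.2, make the earlier date the date of progression instead of a censoring date. Section 4.5.19 uses the first date criteria were met for one route and the day of first suspicion for another; reconcile these into one stated analysis date for each route.
- Censor patients who are alive and progression-free at the last adequate MRI and examination.
- State how suspected but unconfirmed progression is coded if the patient dies or is lost during the confirmation period of about 12 weeks.
- State in 16.2 that missed treatment alone does not censor a patient who is still followed.
- Censor OS at the date last known alive.
- Add a sensitivity analysis that censors deaths after a long gap without assessment at the last adequate evaluation, with the length of the gap fixed in advance.

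The cost is wording. Survival follow-up already seeks vital status, though it may be missing for a patient who is truly lost. PFS may look slightly less favourable, and a death after a gap may be dated later than the true progression, which the sensitivity analysis is there to show.
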